2.3 Rationale

Multiple considerations support the argument that combining an NAE inhibitor such as MLN4924

[figure not shown]

Figure 1. A hypothetical model summarizing mechanism of action underlying interactions between HDACis

(pevonedistat), with an HDACi could be effective in relapsed/refractory AML, based on reciprocal interactions. First, it exploits the NF- κ B-inhibitory capacity of MLN4924 (pevonedistat) (Swords *et al.*, 2010a) to disable an important HDACi compensatory cytoprotective response of AML cells (Dai *et al.*, 2005). Importantly, NF- κ B interruption diminishes AML leukemia-initiating cell (LIC) survival (Guzman *et al.*, 2002).

Moreover, both HDACi (Rosato *et al.*, 2003) and MLN4924 (pevonedistat) (Swords *et al.*, 2010) induce oxidative injury and DNA damage in AML cells. Second, MLN4924 (pevonedistat)-induced DNA damage results in multiple DNA-damage checkpoint and repair processes (*e.g.*, Chk1 and Wee1 activation) (Blank *et al.*, 2013), events

known to be antagonized by HDACi (Brazelle *et al.*, 2010). Thus, HDACis may reciprocally increase MLN4924 (pevonedistat) anti-leukemic activity by blocking DNA-damage responses (*e.g.*, checkpoint or DNA repair). Third, certain poor prognosis genetic aberrations (*e.g.*, p53 deficiency or FLT3-internal tandem duplication [FLT3-ITD]) are associated with impaired DNA checkpoints or repair (*e.g.*, defective HR) (Fan *et al.*, 2010), which could render them particularly susceptible to this strategy. Finally, aside from PIs, MLN4924 (pevonedistat) is the first clinically relevant new-generation NF- κ B antagonist available, and in sharp contrast to bortezomib, has significant anti-leukemic activity itself (Swords *et al.*, 2010b). A model of proposed reciprocal interactions between NAE and HDACi is shown in Figure 1. In summary, MLN4924 (pevonedistat) blocks NF- κ B and the intra-S-phase checkpoint in HDACi-treated cells; conversely, HDACis block checkpoints (Chk1/Wee1/ATR) and disrupt HR (Ladd *et al.*, 2013) and NHEJ (Koprinarova *et al.*, 2011) in malignant cells, leading to enhanced DNA damage and cell death.

In support of these concepts, we have very recently reported that MLN4924 (pevonedistat) and HDACi (*e.g.*, belinostat) interact in a highly synergistic manner in AML cells, particularly in p53 and/or FLT3-ITD mutant cells, as well as primary AML blasts (Zhou *et al.*, 2016). Notably, the basis for synergism appears to be reciprocal in that MLN4924 (pevonedistat) inhibits NF- κ B and disrupts the intra-S-phase checkpoint, events known to increase HDACi lethality. Conversely, HDACi block checkpoint (Wee1, Chk1) and repair (*e.g.*, both HR and NHEJ) responses induced by MLN4924 (pevonedistat), and dramatically potentiate DNA damage. Moreover, similar interactions occurred in AML populations enriched for LICs (CD34+/CD38-/CD123+), but not in normal progenitors. Importantly, the MLN4924 (pevonedistat)/belinostat regimen very significantly increased survival in a systemic human xenograft AML model (MV4-11) while exerting minimal toxicity (*e.g.*, weight loss). The collective findings support further investigation of the MLN4924 (pevonedistat) and belinostat combination in AML.

As MLN4924 (pevonedistat) and belinostat have not been combined together in humans previously, a true assessment of toxicity is limited. Based on the available information, there is limited overlapping toxicity. Both drugs have evidence of hematologic toxicity including anemia and neutropenia which are generally acceptable toxicities in the AML population given the underlying pathology. While hepatic toxicity (elevated aspartate aminotransferase [AST]/ alanine aminotransferase [ALT]) was more common with MLN4924 (pevonedistat), it is less common with belinostat. Additionally, both drugs are associated with fever. Section 10.1 of the protocol provides a comprehensive list of known toxicities of each agent. The limited overlapping toxicity with known preclinical activity provides further support of investigation of the MLN4924 (pevonedistat) and belinostat combination in AML.

2.4 Correlative Studies Background

[REDACTED]

The following represent the candidate pharmacodynamic biomarkers, along with the assessment time-points and the objectives of our studies:

[REDACTED]

- [REDACTED]

[REDACTED]

[REDACTED]

• [REDACTED]

HDACi increase the levels of pro-apoptotic [REDACTED]

• [REDACTED]

[REDACTED]

• [REDACTED]

[REDACTED]

• [REDACTED]

[REDACTED]

• [REDACTED]

[REDACTED]

- Pre- and post-treatment (6-hr) NAE inhibition in leukemic blasts

Preliminary data indicate that inhibitors of NAE activity may be of therapeutic value in a variety of cancers by preventing neddylation and activation of the CDLs, thus disrupting proteasomal degradation of a variety of critical regulatory proteins integral to tumor cell growth, proliferation, and survival. We will determine whether markers of NAE inhibition are present in leukemic blasts collected from patients approximately 6 hrs after receiving MLN4924 (pevonedistat) and belinostat.

2.5 Pharmacokinetic Studies Background

PK analysis of MLN4924 (pevonedistat) and belinostat will be performed with three goals: 1) to gain preliminary insights into potential PK interactions between the two agents; 2) to determine whether plasma drug levels can be achieved that mimic concentrations shown to be active in previous *in vitro* studies; and 3) to obtain preliminary information concerning correlations between PK parameters (*e.g.*, drug exposure) and results of pharmacodynamic studies and/or responses, if the latter occur.

See Section 5 for further details on operational characteristics of PK studies.

3. PATIENT SELECTION

3.1 Inclusion Criteria (all of the following criteria must be met for enrollment)

3.1.1 Patients must have one of the following, histologically or cytologically confirmed:

- AML (non- acute promyelocytic leukemia [APL] AML)
 - AML that is relapsed or refractory to at least one prior line of therapy
- MDS, must meet all of the following at the time of enrollment:
 - Higher risk MDS (intermediate-2 or high risk by the original IPSS) (Greenberg *et al.*, 1997), and
 - Relapsed, refractory, or intolerant to at least one prior line of therapy containing a hypomethylating agent (DNA methyltransferase inhibitor).

3.1.2 Age ≥ 18 years.

Because no dosing or adverse event data are currently available on the use of MLN4924 (pevonedistat) in combination with belinostat in patients < 18 years of age, children are excluded from this study, but will be eligible for future pediatric trials.

3.1.3 ECOG performance status ≤ 2 (Karnofsky $\geq 60\%$, see Appendix A).

3.1.4 Patients must have adequate organ and marrow function as defined below:

- | | |
|--|---|
| – total bilirubin | \leq upper limit of normal (ULN) for the laboratory except in patients with Gilbert's syndrome. Patients with Gilbert's syndrome may enroll if direct bilirubin $\leq 1.5 \times$ ULN for the laboratory of the direct bilirubin. |
| – AST(SGOT)/ALT(SGPT) | $\leq 3 \times$ institutional ULN. |
| – creatinine clearance | Within normal limits for the laboratory |
| OR | |
| – estimated glomerular filtration rate (GFR) | ≥ 60 mL/min/1.73 m ² appropriate to race for patients |

with creatinine levels above institutional normal.

- 3.1.5 Known human immunodeficiency virus (HIV) positive patients who meet the following criteria will be considered eligible:
- CD4 count >350 cells/mm³
 - Undetectable viral load
 - Maintained on modern therapeutic regimens utilizing non-CYP-interactive agents
 - No history of Acquired Immune Deficiency Syndrome (AIDS)-defining opportunistic infections
- 3.1.6 If evidence of chronic hepatitis B virus (HBV) infection, HBV viral load must be undetectable on suppressive therapy, if indicated.
- 3.1.7 If history of hepatitis C virus (HCV) infection, patients must be treated and have an undetectable HCV viral load.
- 3.1.8 The effects of belinostat and/or MLN4924 (pevonedistat) on the developing human fetus are unknown. For this reason and because histone deacetylase inhibitors and NAE inhibitory agents are known to be teratogenic, women of child-bearing potential and men must use 1 highly effective method and 1 additional (barrier) method of contraception at the same time, from the time of signing the informed consent through 4 months after the last dose of study drug (female and male condoms should not be used together). Should a woman become pregnant or suspect she is pregnant while she or her partner is participating in this study, she should inform her treating physician immediately. Men treated or enrolled on this protocol must also agree to use adequate contraception prior to the study, for the duration of study participation, and 4 months after completion of MLN4924 (pevonedistat) and belinostat administration.
- 3.1.9 Ability to understand and the willingness to sign a written informed consent document. Participants with impaired decision-making capacity (IDMC) who have a legally-authorized representative (LAR) and/or family member available will also be eligible.

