2.2.1.2 Clinical Experience with Belinostat

Belinostat (PXD101, Beleodaq, Spectrum Pharmaceuticals, Inc.), FDA-approved in 2014 for relapsed/refractory peripheral T-cell lymphoma (PTCL), is a hydroxamate derivative that inhibits both class I and II HDACs (pan-HDACi) (Molife *et al.*, 2011). In preclinical studies, it suppresses the growth of and induces apoptosis in a variety of tumor types, both *in vitro* and *in vivo* (Plumb *et al.*, 2003; Qian *et al.*, 2006; Qian *et al.*, 2008; Buckley *et al.*, 2007; Ma *et al.*, 2010). Although the drug has mostly been administered intravenously (IV) in clinical trials, an oral formulation has also been tested (Steele *et al.*, 2011). IV belinostat displays linear PKs with respect to the maximum concentration (C_{max}) and the area under the “concentration time” curve (AUC) (Steele *et al.*, 2008), without significant accumulation (Yeo *et al.*, 2012). The intermediate elimination half-life is 0.3 to 1.3 hrs and independent of dose (Steele *et al.*, 2008). Belinostat PKs are unaltered by concurrent administration with carboplatin and paclitaxel (Lassen *et al.*, 2010). Glucuronidation by UGT1A1 is by far the major route of belinostat elimination in humans (Wang *et al.*, 2013). The drug has 5 major metabolites, which are not expected to have anticancer effects, and the parent drug and metabolites can be quantified in human plasma by means of a validated liquid chromatography-tandem mass spectrometry assay (Kiesel *et al.*, 2013). *In vitro* studies indicate that belinostat is a weak/moderate inhibitor of cytochrome P450 family 2 subfamily C member 8 (CYP2C8) and a moderate to strong inhibitor of CYP2C9.

In a phase 1 study in patients with advanced solid tumors, the MTD of belinostat was 1000 mg/m²

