3.2 Exclusion Criteria (none of the following may be present for enrollment)

- 3.2.1 Clinical picture indicative of leukostasis or evidence of disseminated intravascular coagulopathy.
- 3.2.2 Uncontrolled coagulopathy or bleeding disorder.
- 3.2.3 Systemic antineoplastic therapy or radiotherapy for other malignant conditions within 14 days before the first dose of any study drug, except for hydroxyurea.
- 3.2.4 Uncontrolled high blood pressure (*i.e.*, systolic blood pressure >180 mm Hg, diastolic blood pressure >95 mm Hg).

- 3.2.5 Female patients who intend to donate eggs (ova) during the course of this study or 4 months after receiving their last dose of study drug(s).
- 3.2.6 Male patients who intend to donate sperm during the course of this study or 4 months after receiving their last dose of study drug(s).
- 3.2.7 Ongoing toxicities \geq grade 2 from prior therapy, except those related to hydroxyurea (which is permitted through the first 5 days of study treatment).
- 3.2.8 APL (M3).
- 3.2.9 Active central nervous system (CNS) leukemia.
- 3.2.10 History of allergic reactions attributed to compounds of similar chemical or biologic composition to MLN4924 (pevonedistat) or belinostat.
- 3.2.11 Stem cell transplant within previous 3 months prior to initiation of study therapy.
- 3.2.12 Major surgical procedures \leq 28 days before beginning study treatment or minor surgical procedures \leq 7 days before beginning study treatment. No waiting required after placement of a vascular access device.
- 3.2.13 Uncontrolled intercurrent illness or infection.
- 3.2.14 Circulating blast count $>50,000 \text{ mm}^3$ within 7 days preceding enrollment.
- 3.2.15 Current candidacy for a potentially curative allogenic stem cell transplant, unless declined.
- 3.2.16 Left ventricular ejection fraction (LVEF) $<50\%$ as assessed by echocardiogram or radionuclide angiography.
- 3.2.17 Prolongation of the heart-rate corrected QT (QTc) interval $\geq 450 \text{ ms}$ (*i.e.*, grade 1 or higher) on electrocardiogram (ECG) prior to initiation of study treatment.
 - If baseline QTc on screening ECG is $\geq 450 \text{ ms}$ (*i.e.*, grade 1 or higher):
 - Check potassium and magnesium serum levels, and
 - Correct any identified hypokalemia and/or hypomagnesemia and repeat ECG to confirm QTc interval.

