 - For patients with baseline heart rate $<60 \text{ bpm}$ or $>100 \text{ bpm}$, manual measurement of QT interval by cardiologist is required, with Fridericia correction applied to that manual measurement to determine the QTc for eligibility consideration.

Note: For patients with a heart rate of 60-100 bpm, manual measurement of QT interval and use of the Fridericia formula to determine QTc is NOT required.

3.2.18 Known cardiopulmonary disease defined as:

- Unstable angina;
- Congestive heart failure (New York Heart Association [NYHA] Class III or IV; see Appendix B);
- Myocardial infarction (MI) within 6 months prior to first dose (patients who had ischemic heart disease such as ACS, MI, and/or revascularization greater than 6 months before screening and who are without cardiac symptoms may enroll);
- Symptomatic cardiomyopathy;
- Clinically significant pulmonary hypertension requiring pharmacologic therapy
- Clinically significant arrhythmia defined as any of the following:
 - History of polymorphic ventricular fibrillation or torsade de pointes
 - Permanent atrial fibrillation (a fib), defined as continuous a fib for ≥ 6 months
 - Persistent a fib, defined as sustaining a fib lasting > 7 days and/or requiring cardioversion in the 4 weeks before screening
 - Grade 3 a fib defined as symptomatic and incompletely controlled medically, or controlled with device (e.g., pace maker), or ablation in the past 6 months
 - Patients with paroxysmal a fib or $<$ Grade 3 a fib for a period of at least 6 months are permitted to enroll provided that their rate is controlled on a stable regimen
 - Known congenital long QT syndrome.
 - Second degree atrioventricular (AV) block type II or third degree AV block
 - Ventricular rate <50 bpm or > 120 bpm.

3.2.19 Treatment with clinically significant metabolic enzyme inducers within 14 days before the first dose of the study drug.

Note: Because the lists of these agents are constantly changing, it is important to regularly consult a frequently-updated medical reference. As part of the enrollment/informed consent procedures, the patient will be counseled on the risk of interactions with other agents, and what to do if new medications need to be prescribed or if the patient is considering a new over-the-counter medicine or herbal product.

3.2.20 Ongoing or planned treatment with strong inhibitors of UGT1A1.

3.2.21 Any known *UGT1A* polymorphism, heterozygous or homozygous.

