5.2.3 Overview of Process at Treating Site

5.2.3.1 OPEN Registration

All registrations will be performed using the Oncology Patient Enrollment Network (OPEN) system. OPEN communicates automatically with the Interactive Web Response System (IWRS) which handles identifier assignments, any study randomization and any prescribed slot assignments. If specimen analysis is required to determine eligibility, the protocol will be setup with multi-step registration.

Registration without eligibility specimen analysis:

1. Site enters registration data into OPEN during one or more steps.
2. IWRS receives data from OPEN, generates the Patient Study ID and the Universal Patient ID, both of which are sent back to OPEN.
3. IWRS sends all applicable registration data directly to Rave at the end of the final registration step.

Registration with eligibility specimen analysis - *not applicable for this trial.*

Any data entry errors made during enrollment should be corrected in Rave.

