6. TREATMENT PLAN

6.1 Agent Administration

This will be a two-part phase 1 dose-escalation and exploratory dose-expansion study of MLN4924 (pevonedistat) in combination with belinostat. Part A will consist of a 3+3 dose-escalation phase of the combination to assess its safety and tolerability and identify an MTD/tentative RP2D. After the MTD has been established, Part B of the study will involve an exploratory-dose expansion study of 12 additional patients who will be enrolled at the tentative RP2D to gain further insights into the safety of the regimen. MLN4929 (pevonedistat) and belinostat dose rounding is allowed per institutional guidelines.

Treatment will be administered on an outpatient basis. Cycles are to be repeated every 21 days. Reported adverse events and potential risks are described in Section 10. Appropriate dose modifications are described in Section 7. Other than hydroxyurea during the first 5 days of study treatment, no investigational or commercial agents or therapies other than those described below may be administered with the intent to treat the patient's malignancy.

Dose Escalation Schedule				
Dose Level	Belinostat		MLN4924 (pevonedistat)	
	Dose (mg/m²/day)	Administration and Schedule	Dose (mg/m²/day)	Administration and Schedule
-1	800	Intravenously over 30 minutes once daily on Days 1-5 of each 21-day cycle	15	Intravenously over 60 minutes once daily on Days 1, 3, & 5 of each 21-day cycle**
1*	800		20	
2	800		25	
3	800		37	
4	1000		37	
5	1000		50	
6***	1000		59	

* Starting dose level

** When both drugs are given on the same day (Days 1, 3, 5), start the MLN4924 (pevonedistat) infusion within 60 mins after the completion of belinostat infusion.

*** The 59 mg/m² level will not begin until the NCI/CTEP, Principal Investigator and Takeda have closely examined the toxicity, PK and clinical data from the 50 mg/m² cohort. Takeda must give written approval for the 59 mg/m² to begin.

Regimen Description				
Agent	Premedication; Precautions	Dose And Route	Schedule	Cycle Length
Belinostat	See Section 6.4	In 250 mL 0.9% NaCl IV over 30 (± 5 min)*** Dose per assigned dose level.	Days 1-5 (week 1)	21 days (3 weeks)
MLN4924 (pevonedistat)	See Section 6.4	In 250 mL D5W or 0.9% NS IV over 60 min (± 10 min)* Infusion to start within 60 minutes after belinostat infusion ends. Dose per assigned dose level.	Days 1, 3, & 5 (week 1)**	

IV = Intravenously; D5W = dextrose 5% in water; NS = normal saline.

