Potential Drug Interactions: Belinostat is primarily metabolized by hepatic UGT1A1, and to a lesser extent by CYP2A6, CYP2C9 and CYP3A4 enzymes. Avoid concomitant use of strong inhibitors of UGT1A1. Use caution when co-administering agents which may compete for UGT1A1 metabolism, such as irinotecan. Patients with known UGT1A1 genetic polymorphisms, such as UGT1A1*28, can have reduced UGT1A1 activity and may be at risk for increased belinostat exposure. If subjects with UGT1A1 genetic polymorphisms are not excluded from study participation, reduced doses are warranted.

In vitro studies have shown belinostat and its metabolites are weak to moderate inhibitors of CYP2C8 and moderate to strong inhibitors of CYP2C9; however, studies did not demonstrate effects when co-administered with warfarin. Avoid CYP2C8 and CYP2C9 substrates during belinostat treatment unless deemed medically necessary.

Belinostat is likely a P-gp substrate but is unlikely to inhibit P-gp.

Avoid concomitant medications that may cause Torsade de Pointes.

Availability: Belinostat is an investigational agent supplied to investigators by the DCTD, NCI. Belinostat is provided to the NCI under a Collaborative Agreement between the Pharmaceutical Collaborator and the DCTD, NCI (see Section 13).

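### Section 3.1.4 admits Gilbert's syndrome with no total bilirubin ceiling, although Sections 3.2.20, 3.2.21 and 8.1.2 aim to keep reduced UGT1A1 activity away from the full belinostat dose

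*Combined protocol and SAP*

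**What the plan says.** **Who may enter.** Section 3.1.4 requires total bilirubin at or below ULN, then exempts one group: "Patients with Gilbert's syndrome may enroll if direct bilirubin" does not exceed 1.5 × ULN. No total bilirubin limit is given for them.

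**Who may not.** Section 3.2 is headed with the condition "none of the following may be present for enrollment". Item 3.2.20 lists "Ongoing or planned treatment with strong inhibitors of UGT1A1". Item 3.2.21 lists "Any known *UGT1A* polymorphism, heterozygous or homozygous".

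**Why UGT1A1 matters.** Section 2.2.1.2 states: "Glucuronidation by UGT1A1 is by far the major route of belinostat elimination in humans". Section 8.1.2 says that patients with known UGT1A1 polymorphisms can have reduced enzyme activity and may be at risk of higher belinostat exposure. It adds: "If subjects with UGT1A1 genetic polymorphisms are not excluded from study participation, reduced doses are warranted".

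**What dose is given.** The Section 6.1 regimen table gives belinostat as "Dose per assigned dose level", which is 800 mg/m² at levels -1 to 3 and 1000 mg/m² at levels 4 to 6. The Section 7.1 steps go down from that starting dose (800 to 600; 1000 to 800 to 600). No section sets a lower first dose for Gilbert's syndrome or for UGT1A1 carriers.

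**The concern.** A Gilbert's exemption for bilirubin is common in oncology eligibility lists, because the raised bilirubin is unconjugated and does not signal liver damage. Here the study drug is itself cleared mainly by the enzyme that is deficient. The exemption therefore names and admits a group that the rest of the protocol tries to keep out.

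Two things are at stake. The first is patient safety: a person who may clear belinostat slowly could receive the full assigned dose in a combination that, according to Section 2.3, had not been given to humans before. The second is consistency: the protocol does not say whether a clinical diagnosis of Gilbert's syndrome makes a UGT1A polymorphism known, so eligibility may depend on which site reads the text.

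**Working it through.** The plan has no figure to reproduce. The check sets the sections side by side.

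**Premise.** The documents do not link Gilbert's syndrome to UGT1A1. The link used here is the standard definition of the condition. Section 3.1.4 fits it: waiving the total bilirubin limit while capping direct bilirubin makes sense when the expected elevation lies in the indirect fraction.

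**Direction of the other provisions.** Strong UGT1A1 inhibitors are excluded (3.2.20). Known UGT1A polymorphisms are excluded, even heterozygous ones (3.2.21). UGT1A1 inhibitors and substrates are discouraged on study (6.5.1). Section 8.1.2 offers two routes for carriers, exclusion or a lower dose. All of these point towards protection; the exemption in 3.1.4 points the other way.

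**Reading A: a clinical Gilbert's diagnosis counts as a known UGT1A polymorphism.** No exclusion may be present, so every such patient is ineligible under 3.2.21. The exemption in 3.1.4 then never applies. No patient is harmed, but the text contradicts itself.

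**Reading B: it does not count unless a genotype is on record.** A Gilbert's patient with a documented genotype is still excluded. One diagnosed clinically and never genotyped is admitted by 3.1.4. The first belinostat dose is the one for the assigned level, because Section 6.1 has no other and the steps in 7.1 are reductions from that start.

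**Choice between readings.** The protocol makes none.

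**Safeguards that remain under Reading B.**
- Section 3.2.27 lets the investigator exclude a patient on grounds of risk.
- Section 11 requires bilirubin to be read before each pevonedistat dose.
- Section 5.3.3 makes Cycle 1 PK sampling mandatory.
- AST and ALT limits (3.1.4) and the cirrhosis exclusion (3.2.24) still apply.

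None of these sets a lower first belinostat dose.

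**Number affected.** The documents do not give the frequency of Gilbert's syndrome. Taking 1% to 10% purely as an assumption, the Part A maximum of 30 patients (Section 9.2) would include 30 × 0.01 = 0.3 to 30 × 0.10 = 3.0 with the condition. The group at issue under Reading B is a subset of these: diagnosed, not genotyped, otherwise eligible and not excluded by discretion. The range is too wide to say more than that the number is probably small.

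**The case against.** The strongest reply is that Section 8.1.2 offers a choice between excluding carriers and lowering their dose, and that the protocol chose exclusion. The absence of a reduced starting dose follows from that choice. The exposure warning in 8.1.2 is also worded for patients with known polymorphisms, so a patient who falls outside 3.2.21 because nothing is known arguably falls outside 8.1.2 as well. This stands in part. A reader might infer a literal breach of 8.1.2, and the wording does not support that. What remains is a conflict with the protective purpose of 3.2.20, 3.2.21 and 8.1.2.

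Three further inferences are tempting and should not be drawn.

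- *No genotype can be known at entry.* The line "Registration with eligibility specimen analysis - *not applicable for this trial" in Section 5.2.3.1 describes how registration is set up. It says nothing about genotype results already in a patient's record, and parts of the biomarker plan are redacted, so the absence of genotyping cannot be asserted.
- *Levels 4 to 6 leave no safety margin because 1000 mg/m² is the single-agent MTD.* Section 2.2.1.2 also reports 1000 mg/m² on Days 1-5 and 8-12 with bortezomib as tolerable, and no MTD reached at 2000 mg/m² with 13-cis retinoic acid. Without a figure for the exposure increase, the margin cannot be judged.
- *Baseline bilirubin would be counted as a DLT.* Section 7.2.2 does grade bilirubin against ULN regardless of baseline. But Section 6.2 requires the event to be considered related to treatment, Section 7.2.1 requires no dose modification for unrelated events, and Section 7.3 allows a new cycle at baseline values. Misclassification is speculative.

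It is also fair to say that the link between Gilbert's syndrome and UGT1A1 comes from outside the protocol. It is a definition rather than a study result, and it is declared here as a premise.

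**Conclusion.** The two eligibility lines conflict. Under one reading the Gilbert's exemption has no effect. Under the other it admits clinically diagnosed, ungenotyped patients at the full assigned belinostat dose, although the protocol elsewhere keeps reduced UGT1A1 activity out on exposure grounds. Because the text does not choose, sites may decide alike patients differently.

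The conclusion rests on the standard definition of Gilbert's syndrome. The documents do not give the size of any exposure increase or the number of patients affected, and that number is probably small. The documents do not support a claim that the MTD or the recommended phase 2 dose would be biased. Severity is minor to moderate; it merits correction because the correction is cheap and errs towards safety.

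**What to change.** Make two changes to the eligibility text:

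1. In 3.1.4, delete the Gilbert's exemption, so that total bilirubin at or below ULN applies to every patient.
2. In 3.2.21, state that a clinical diagnosis of Gilbert's syndrome counts as a known UGT1A polymorphism.

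The cost is a two-sentence amendment with no new tests. A few Gilbert's patients become ineligible. Carriers who have never been genotyped and have normal bilirubin would still enter, so the change does not close every route to higher exposure.

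If the investigators prefer to keep Gilbert's patients, the alternative is larger: a total bilirubin ceiling, UGT1A1 genotyping and a defined lower belinostat starting dose. Only declaring that a clinical diagnosis does not count under 3.2.21 would make sites consistent, but would leave those patients at the full assigned dose.
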